## 7.2 Final Analysis

The final analysis will occur after all subjects reach the end of study.

Data will be subject to ongoing checks for integrity, completeness and accuracy in accordance with the Data Management Plan with the expectation that outstanding data issues are resolved ahead of the lock. The data supporting the final analysis will be locked to prevent further changes.

## 8. Data Screening and Acceptance

### 8.1 General Principles

The objective of the data screening is to assess the quantity, quality, and statistical characteristics of the data relative to the requirements of the planned analyses.

### 8.2 Data Handling and Electronic Transfer of Data

The Amgen Global Study Operations-Data Management (GSO-DM) department will provide all data to be used in the planned analyses. This study will use the RAVE database. All laboratory, PK, [REDACTED] and biomarker data from the central laboratory or vendor will be transferred to GSO-DM. SLE efficacy assessment and PRO data from the central vendor will be transferred to GSO-DM. All other data will be captured on the eCRF.

### 8.3 Handling of Missing and Incomplete Data

Subjects may have missing specific data points for a variety of reasons. In general, data may be missing due to a subject's early withdrawal from study, a missed visit, or non-evaluability of a specific clinical or laboratory measurement at its planned clinical visit.

**Additionally, as the study was terminated before the planned completion, subjects may have missed clinical visits including not completing the week 52 visit. For efficacy and PRO outcomes, subjects who terminated early due to sponsor decision will be excluded from analyses of data from visits for which they did not have the opportunity to participate in by the date of study termination decision being communicated to sites, i.e. April 5, 2023. Efficacy data collected after this date will be censored and excluded from analyses for that particular visit.** Unless specified, no imputation will be used. The general procedures outlined below describe what will be done when a data point is missing.

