7.2.1 Reasons for Removal From Study

Reasons for removal of a subject from the study are:

- Decision by sponsor*
- Withdrawal of consent from study
- Death
- Lost to follow-up

* Study discontinuation of 'decision by sponsor' will only be used in the event that the study is terminated, for any reason, including due to futility. Subjects who are still on study at the time of that decision may be terminated per sponsor decision.

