8.1.2 Treatment Period

Visits will occur per the Schedules of Activities (Table 1-2 and Table 1-3). The date of the first dose of investigational product is defined as day 1. All subsequent doses and study visits will be scheduled based on the day 1 date. The investigational product is to

be administered following the completion of all other study required procedures for that visit.

If a subject discontinues investigational product prior to week 52, the subject will be encouraged to maintain the planned scheduled assessments through week 52 ([Table 1-3](#)). If the subject discontinues the study completely prior to week 52, the subject should complete an early termination (ET) visit (ie, week 52 visit procedures) which must be scheduled to allow for at least 6 weeks for safety data collection after last dose of investigational product.

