8.1.4 End of Study

Refer to Section [4.4](#) for End of Study definition.

All end of study procedures (ie, week 52/ET visit) should be performed at the final visit for subjects who discontinue study before week 52.

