## 6. Analysis Sets

### 6.1 Full Analysis Set

The Full Analysis Set (FAS) includes all randomized subjects. Data will be analyzed based on randomized treatment assignment.

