#### Hybrid SLEDAI

In case of completely missing hSLEDAI assessment (e.g. missed visit) or partially missing (e.g. laboratory measurements not available), the missing post-baseline hSLEDAI total score will be imputed using last observation carried forward (LOCF) if the previous analysis visit is not missing. Baseline hSLEDAI will not be carried forward to post-baseline.

The hSLEDAI total score will then be computed based on the non-missing and imputed data. **If the hSLEDAI total score cannot be evaluated after imputation, the hSLEDAI score  $\geq 4$  points reduction from baseline will be considered not met.**

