## CLASI

**In case of completely missing CLASI assessment (e.g. missed visit) or partially missing, the missing post-baseline CLASI items will be imputed using LOCF if the previous analysis visit is not missing. Baseline CLASI will not be carried forward to post-baseline.**

**The CLASI activity score will then be computed based on the non-missing and imputed data. If the CLASI activity score cannot be evaluated after imputation, the CLASI activity score  $\geq 50\%$  improvement endpoint will be considered not met.**

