## SRI-4, BICLA and LLDAS

The criteria for SRI-4, BICLA and LLDAS responses will be evaluated based on the non-missing and imputed PGA, hSLEDAI and BILAG data. If any criteria based on the non-missing and imputed PGA, hSLEDAI and BILAG data cannot be evaluated, then the subject will be considered as a non-responder.

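### SAP 8.3 drops not-yet-due subjects from a visit only if the sponsor ended their participation; those who had already left for other reasons stay in the denominator, mostly as non-responders

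*SAP*

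**What the plan says.** SAP 8.3 (general paragraph) sets two conditions for leaving a subject out of a visit. The rule is that "subjects who terminated early due to sponsor decision will be excluded from analyses of data from visits for which they did not have the opportunity"; opportunity is judged at the date the termination decision reached sites, 5 April 2023. Both conditions must hold: the exit reason and the date.

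Protocol 7.2.1 limits the exit reason: "Study discontinuation of 'decision by sponsor' will only be used in the event that the study is terminated". Consent withdrawal, death and loss to follow-up are separate reasons there.

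Efficacy is analysed on the Full Analysis Set (SAP 9.5), and "The Full Analysis Set (FAS) includes all randomized subjects" (SAP 6.1). Missing visits are then handled in SAP 8.3 as follows:

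- hSLEDAI: "missing post-baseline hSLEDAI total score will be imputed using last observation carried forward (LOCF) if the previous analysis visit is not missing". Baseline is not carried forward, and otherwise the 4-point reduction is not met. BILAG and PGA VAS have the same previous-visit condition.
- SRI-4, BICLA and LLDAS: if any criterion "cannot be evaluated, then the subject will be considered as a non-responder".
- CLASI: "If the CLASI activity score cannot be evaluated after imputation", the 50% improvement is not met.
- Joint counts: proration for non-evaluable joints, no carry-forward, otherwise not met.

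Protocol 8.1.4 adds that end-of-study procedures "should be performed at the final visit for subjects who discontinue study before week 52". An early-termination visit can therefore supply data for whichever Appendix D window it falls in.

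**The concern.** The rule selects the denominator on something that happens after randomisation. Take two subjects randomised on the same day in January 2023. Neither could reach week 52, due in January 2024, before the stop. The one still on study at termination is removed from week 52. The one who withdrew consent in March 2023 is kept, almost certainly as a non-responder. Among subjects not yet due, the rule discards those who might have responded and keeps those who had already left.

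SAP Section 10 drops all treatment comparisons, and Tables 9-1 and 9-2 give the number and percentage responding per arm. Those percentages are the remaining response result for SRI-4, BICLA, LLDAS, hSLEDAI, CLASI and joint counts. SAP 9.2 tabulates discontinuation reasons by arm but not how many leavers were not yet due at each visit, so a reader cannot undo the effect.

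**Working it through.** **1. Does anything else remove the early leaver?** No. SAP 6.1 and 9.5 keep all randomised subjects, and the instrument-specific rules in 8.3 only assign values. By contrast, SAP 6.3 defines the interim sets by opportunity to complete week 16, with no condition on exit reason. Read literally, 8.3 also keeps a subject who left for another reason after 5 April but before being exited by the sponsor.

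**2. Effect on the percentage.** Let D be the subjects due at a visit, p their response rate, k the retained leavers not yet due, and r the response rate assigned to them.

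Reported rate = (D·p + k·r)/(D + k), so shift = p − reported rate = (p − r)·k/(D + k).

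The shift is downward when k > 0 and r < p, and zero when k = 0. The plan states no figure to reproduce. Inputs: p = 40% is the placebo rate in SAP 3.2. D = 26 is 25% of the 104 subjects at the third interim in SAP Table 3-1, a week 24 count used only for scale. The other D, k and r values are assumptions.

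| D | k | Shift at r = 0 | Shift at r = 0.3 |
|---|---|---|---|
| 26 | 1 | 0.40 × 1/27 = 1.48 points | 0.10 × 1/27 = 0.37 |
| 20 | 1 | 0.40 × 1/21 = 1.90 | 0.10 × 1/21 = 0.48 |
| 20 | 3 | 0.40 × 3/23 = 5.22 | 0.10 × 3/23 = 1.30 |

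**3. How large might k be?** Assume exponential withdrawal of d over 52 weeks, a share f of the arm due at week 52, and follow-up of the rest uniform up to that point. The expected fraction of not-yet-due subjects who have left is q = 1 − d/(−ln(1 − d)), and k/D = q(1 − f)/f.

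- f = 0.5, d = 0.05: q = 0.0252, k/D = 0.0252, shift at r = 0 is 0.40 × 0.0252/1.0252 = 1.0 points.
- f = 0.3, d = 0.20: q = 0.1037, k/D = 0.242, shift at r = 0 is 0.40 × 0.242/1.242 = 7.8 points.

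**4. Simulation with the SAP's rules** (d = 5, 10, 20%; f = 50, 40, 30%; visits at target ±5 days; response constant over time; rate among due subjects set to 40%):

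| Carry-forward and early-termination (ET) visits | r | Week 52 shift, points |
|---|---|---|
| One-step, no ET visits | 0.003-0.004 | 0.9-7.5 |
| One-step, all leavers attend ET | 0.006-0.011 | 1.0-7.4 |
| Chained, no ET visits | 0.34 | 0.1-1.1 |
| Chained, all attend ET | 0.40 | about 0 |
| None (joint counts), all attend ET | 0.001 | 0.9-7.6 |

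The upper one-step values lie slightly below the closed form. The main reason is that continuers who attended week 52 on days 360-369 are also counted under the SAP rule. Earlier visits shift less with one-step carry-forward: 0.3-2.5 points at week 36 and 0.1-0.9 at week 24.

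**5. A second simulation under different assumptions** (40 per arm, follow-up uniform over 2-90 weeks, 45% response, one-step carry-forward). More than 99% of retained leavers counted as non-responders. Mean week 52 response, date-only rule against SAP rule, was 43.0% against 41.6% at 5% annual leaving (1.4 points), 41.0% against 38.4% at 10% (2.6), and 36.7% against 32.2% at 20% (4.5).

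**The case against.** **The size depends on how carry-forward is read.** This stands. SAP 8.3 does not say whether an imputed visit can itself be carried forward. If it can, the shift nearly vanishes for endpoints that use carry-forward. But the condition that the previous analysis visit is not missing reads most naturally as one step, and joint counts have no carry-forward under either reading.

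**No document figure supports the magnitude.** Also true. Withdrawal, number due and early-termination attendance are all assumed, and the top of the range needs 20% withdrawal together with only 30% due.

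**Little turns on it.** The trial had already stopped, no test remains, and the between-arm direction is not fixed. The interim futility decision, the patient-reported change scores and the corticosteroid-reduction endpoint are not shown to be affected. This limits the severity but does not make the percentages correct.

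**Counting leavers as failures is a normal convention.** It is, and leavers whose visit was due remain failures under either rule. The fault is keeping not-yet-due leavers while removing the not-yet-due continuers who belong in the same denominator.

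**A strict date rule discards attended visits.** It does, to a small extent. Subjects with study day 1 from 2 to 11 April 2022 could have attended week 52 within ±5 days by 5 April 2023, or up to 20 April 2022 using the wider Appendix D window. SAP 6.3 would admit them on actual attendance. Doing so, however, brings back some selection on who stayed.

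**Conclusion.** The concern holds and should be fixed. Followed as written, SAP 8.3 applies the opportunity cutoff to one exit reason only and biases the per-arm response percentages downward whenever not-yet-due leavers exist and respond at less than the rate among those due. That the wording does this is certain. The size is not: about 1 to 7.4 points for week 52 SRI-4 under one-step carry-forward with early-termination visits and the assumed withdrawal and due shares, about 0 to 1.1 under chaining, and zero if no such leavers exist. The amount may differ by arm in either direction. No test or type I error is involved.

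**What to change.** In SAP 8.3, delete the condition on sponsor decision and define each visit's denominator by due date alone. Include a Full Analysis Set subject at a visit only if the end of its protocol window (target day + 5) fell on or before 5 April 2023, whatever the reason for leaving and whether or not the visit was attended. The latest qualifying study day 1 is 5 April 2023 minus (target day + 4) days:

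| Visit | Window end | Study day 1 on or before |
|---|---|---|
| Week 52 | Day 370 | 1 April 2022 |
| Week 36 | Day 258 | 22 July 2022 |
| Week 24 | Day 174 | 14 October 2022 |
| Week 12 | Day 90 | 6 January 2023 |
| Week 8 | Day 62 | 3 February 2023 |

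Keep the existing carry-forward, non-responder and 5 April censoring rules within that set, and report the number due per arm and visit. In the step 4 simulation this rule returned 39.8-40.2% in every week 52 cell, against the 40% target.

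The cost is one SAP sentence and one date flag per visit. Denominators become slightly smaller, and a few visits attended before their window closed leave the summary; they can be listed. The exact window end is a choice. The essential change is one date rule for every subject.

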#### Hybrid SLEDAI

In case of completely missing hSLEDAI assessment (e.g. missed visit) or partially missing (e.g. laboratory measurements not available), the missing post-baseline hSLEDAI total score will be imputed using last observation carried forward (LOCF) if the previous analysis visit is not missing. Baseline hSLEDAI will not be carried forward to post-baseline.

The hSLEDAI total score will then be computed based on the non-missing and imputed data. **If the hSLEDAI total score cannot be evaluated after imputation, the hSLEDAI score  $\geq 4$  points reduction from baseline will be considered not met.**

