### **Systemic Lupus Erythematosus Responder Index (SRI-4)**

A subject achieves SRI-4 response if all of the following criteria are met:

1.  $\geq 4$ -point reduction from baseline in hSLEDAI score
2. no new BILAG 2004 A and no  $> 1$  new BILAG 2004 B domain scores compared with baseline (e.g. no B, C, D or E scores at baseline becomes an A or no more than 1 C, D or E score at baseline becomes a B)
3.  $< 0.3$ -point deterioration from baseline in PGA VAS (scale 0 to 3).
4. no use of more than protocol-permitted therapies (i.e. requiring a dose of systemic steroid [for e.g., OCS or intravenous [IV] or intramuscular [IM] corticosteroid] above their baseline dose after week 16; requiring either dose increases of the current immunosuppressants/immunomodulators or initiation of new immunosuppressant/immunomodulatory(s)).

The latest visit date among hSLEDAI, BILAG and PGA VAS will be considered the SRI-4 visit date. In the case when all three visit dates are missing, the upper limit of the analytic window of this visit will be the SRI-4 visit date.

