## BILAG

In case of completely missing BILAG assessment (e.g. missed visit), the missing post baseline BILAG item scores will be imputed using LOCF if the previous analysis visit is not missing.

In case of partially missing, missing laboratory items (e.g. UPCR, creatinine, etc.) will be imputed using LOCF if the previous visit is not missing; other missing items (e.g. active nephritis, Coombs' test positive, etc.) will be imputed as 'No' or 'Not Present'.

Baseline BILAG will not be carried forward to missing post-baseline BILAG.

The BILAG organ domain scores will be calculated based on the non-missing and imputed components. If the non-missing and imputed components are not sufficient to identify the organ domain score, worst scenario approach will be used to determine the BILAG organ domain scores.

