## PGA VAS

Missing post-baseline PGA score will be imputed using LOCF if the score at the previous analysis visit is not missing. Baseline PGA will not be carried forward to missing post-baseline PGA.

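### SAP 8.3 carries the preceding visit forward even after withdrawal or death, so a subject lost just before week 24 or week 52 can be counted as a responder

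*SAP*

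**What the plan says.** SAP 8.3 lists "early withdrawal from study, a missed visit" among the reasons for missing data and then gives rules by instrument.

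- **hSLEDAI:** the "missing post-baseline hSLEDAI total score will be imputed using last observation carried forward (LOCF) if the previous analysis visit is not missing". Also, "Baseline hSLEDAI will not be carried forward to post-baseline".
- **BILAG, when the whole assessment is missing:** "the missing post baseline BILAG item scores will be imputed using LOCF if the previous analysis visit is not missing".
- **PGA VAS:** "Missing post-baseline PGA score will be imputed using LOCF if the score at the previous analysis visit is not missing".
- **CLASI items:** the same previous-visit condition.

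The composites SRI-4, BICLA and LLDAS "will be evaluated based on the non-missing and imputed PGA, hSLEDAI and BILAG data". A subject becomes a non-responder only if a criterion still cannot be evaluated after that step. When the hSLEDAI, BILAG and PGA visit dates are all missing, SAP 5.6 dates the SRI-4 result by rule: "the upper limit of the analytic window of this visit will be the SRI-4 visit date".

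The primary estimand (SAP 2.1) and the SRI-4 definition (SAP 5.6) set only excess corticosteroid or immunosuppressant use to non-response. Neither mentions death, withdrawal of consent or loss to follow-up, all of which protocol 7.2.1 lists as reasons for removal from the study. SAP 8.3 has one rule by reason for leaving: subjects stopped by sponsor decision are excluded from visits they had no opportunity to attend by 5 April 2023.

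**The concern.** Carrying one visit forward is a defensible way to bridge a missed appointment in a subject who is still being followed. Applied to someone who has died or left, it reports a response for a person not on study, in the primary endpoint and several secondary ones. Against a non-response classification it can only raise an arm's rate, and it raises it more where late dropout is more common.

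The SAP is also uneven. For the same absent visit, the flare index stays missing, and a joint count that cannot be evaluated makes the joint endpoint not met. SRI-4 and CLASI response are filled in. The only sensitivity analysis listed for the primary endpoint (SAP Table 9-1) changes the data source, investigator versus adjudicated, so it would not show the effect.

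**Working it through.** The plan states no figure for this point, so the check applies the rule to the SAP's own windows and then sizes it under stated assumptions.

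**1. Reach of the rule.** Efficacy windows from SAP Appendix D: week 20, days 127-154; week 24, days 155-182; week 48, days 323-350; week 52, days 351-394. Because the previous analysis visit must be non-missing:

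- Week 24 can be filled only from a last assessment on days 127-154. A last assessment on day 126 or earlier gives a week 24 non-responder.
- Week 52 can be filled only from a last assessment on days 323-350. A last assessment on day 322 or earlier gives a week 52 non-responder.

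**2. One subject traced through.** A subject meets SRI-4 at the week 48 visit (target day 337), dies on day 340 and has no later data.

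- hSLEDAI, BILAG and PGA VAS are missing at week 52 but present at week 48, so all three are carried forward.
- Every SRI-4 criterion can be evaluated, so the fallback to non-response is not reached.
- No excess therapy was used, so the estimand does not make the subject a non-responder.
- Result: week 52 responder, dated day 394, which is 394 - 340 = 54 days after death.

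The same steps apply from week 20 to week 24, and to BICLA and hSLEDAI response. Week 52 LLDAS follows if the carried hSLEDAI data are taken to serve its descriptor-level criteria, as the composite rule implies. CLASI response is open to it from the visit before each landmark.

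**3. Expected size.** Assumptions, none of them in the documents: annual dropout d of 15-25% at a constant rate. The 40% response is the SAP 3.2 placebo design rate, used as an illustration.

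Share leaving in one 28-day interval = 1 - (1 - d)^(28/365).

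| d | leave in 28 days | x 40% responding |
|---|---|---|
| 15% | 1.2% | 0.5 points |
| 20% | 1.7% | 0.7 points |
| 25% | 2.2% | 0.9 points |

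At 65% response (40% plus the 25-point design difference) the range is 0.8 to 1.4 points. These are upper figures, because they ignore leavers who have observed data in the window.

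**4. Effect of one subject.** The third interim had 104 subjects with the opportunity to reach week 24 (SAP Table 3-1), or 104/4 = 26 per arm if evenly split. Fewer had reached week 52 at that cutoff. With an assumed 20-25 evaluable per arm, one subject moves the rate by 1/25 = 4 to 1/20 = 5 points. The expected number of such leavers per arm is 20 x 1.2% = 0.25 to 25 x 2.2% = 0.55, of whom 0.1 to 0.2 would be counted as responders at 40%.

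**The case against.** Much can be said for the plan, and most of it stands.

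- **The rule is narrow.** A reader might infer that any dropout is carried to week 52. The documents do not support that: the previous-visit condition limits the reach to one visit, baseline is never carried, and if a score still cannot be evaluated the criterion fails.
- **Chaining.** A reader might also infer that an imputed visit counts as not missing, so that values roll on to week 52. With 15-25% dropout and 40% responding at the last visit, that would add 15% x 40% = 6 to 25% x 40% = 10 points. This reading is strained. It would leave the previous-visit condition almost nothing to do, since the ban on carrying baseline already covers subjects with no post-baseline value. It also assumes 40% response among even the earliest leavers. What stands is that the SAP does not rule chaining out in words.
- **Early termination visits.** Protocol Table 1-3 requires one for anyone who leaves the study before week 52, and protocol 8.1.2 places it at least 6 weeks after the last dose. A last dose on day 323 or 337 puts it at day 365 or 379 at the earliest, inside the week 52 window. Many late leavers will therefore have real week 52 data. Deaths, losses and refusals will not. At week 24 the protection is weaker: a last dose on day 141 gives day 183, one day past the window.
- **Sponsor termination.** Subjects stopped by the sponsor are already excluded from visits they could not attend, so carry-forward does not extend them to those visits.
- **No test depends on it.** SAP section 10 removes treatment comparisons from the final analysis.

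**Conclusion.** The gap is real but small. As written, SAP 8.3 can class a subject who has died, withdrawn or been lost as a responder, but only when the subject had data at the analysis visit just before the landmark and none in the landmark window. Under the assumed 15-25% dropout and 40% response, the expected inflation is under about 1 point per arm per landmark. A single case in an assumed arm of 20-25 would move that arm's rate by 4-5 points. Dropout, response among leavers and arm size are all assumptions.

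The issue is minor to moderate. It cannot change a test, because none is planned at the final analysis. It still deserves correcting, because the per-arm count and percentage is now the whole primary result, and the rule misclassifies an outcome that a few words would settle.

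**What to change.** In SAP 8.3, for hSLEDAI, BILAG, PGA VAS and CLASI:

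1. Limit carry-forward to a single intermittent missed or incomplete visit in a subject who is still on study.
2. State that a subject whose death or end-of-study date precedes the visit, for any reason other than sponsor termination, and who has no observed data in that window, is a non-responder at that visit and later ones. Observed early termination data in the window are still used.
3. State that an imputed value is not itself carried forward.

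The cost is a few sentences and one derivation flag built from the end-of-study and death dates. Response rates become slightly lower, and a late leaver who was truly responding will be counted as a non-responder.
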